4.1.2 Randomization of Study Treatment

Not applicable.

4.1.3 Blinding of Study Treatment

This is an open-label study; therefore, blinding is not applicable.

4.1.4 Patient Compliance

Compliance will be assessed by drug intake history. The number of capsules or amount of powder (and way it is subsequently administered, such as yoghurt, juice etc.) as well as the dose (strength) of study drug taken daily and weekly will be captured and this data will be later transcribed into the CRF.

Patients/caregivers judged to be non-compliant will be counselled on the importance of daily intake of study medication, as prescribed. A compliance between 80% - 125% will be desired for the adequate assessment of the study outcomes. Patients who are repeatedly non-compliant or have a compliance of less than outside 80-125% may be discontinued, at investigator's discretion after discussion with the medical monitor. Replacement of subjects will be at sponsor's discretion.

4.1.5 Concomitant Therapy

The Investigator must record in the eCRF any concomitant medication (including indication for the same) taken by the patient during the course of the study. The investigator will use the data from the EDC with information collected by caregivers in between visits.

4.1.5.1 **Prohibited Medications**

Medicinal products which induce torsades de pointes e.g. class Ia, Ic, III antiarrhythmics are prohibited. Other antiarrhythmics (class Ib, II, IV antiarrhythmics) should not be used, unless exceptionally, because of increased risk of adverse cardiac reactions.

CYP1A2 and CYP2D6 inhibitors (CYP1A2 inhibitor: ciprofloxacin, fluvoxamine, propafenone; CYP2D6 inhibitor: propafenone, quinidine) - significantly increases mexiletine exposure and thus the associated risk of adverse reactions to mexiletine.

CYP1A2 and CYP2D6 inducers (CYP1A2 inducer: omeprazole; CYP2D6 inducer: phenytoin, rifampicin) – Decrease the plasma concentration and half-life of mexiletine.

CYP1A2 Substrate such as theophylline, caffeine, lidocaine or tizanidine: Mexiletine is a potent inhibitor of CYP1A2; therefore, co-administration with mexiletine may be associated with elevations in plasma concentrations of the concomitant medicine that could increase or prolong the therapeutic efficacy and/or the adverse reactions of these medications.

The organic cation transporter 2 (OCT2) substrates (such as metformin and dofetilide): If mexiletine and other OCT2 substrates are to be used concurrently, the OCT2 substrate blood levels should be monitored, particularly when the mexiletine dose is changed. An appropriate adjustment in the dose of the OCT2 substrate should be considered.

Drugs with narrow therapeutic window narrow therapeutic window such as digoxin, lithium, phenytoin, theophylline or warfarin.

Any other medications for the treatment of myotonia.

4.2 Investigational Medicinal Product (IMP)

4.2.1 IMP Dosage Form and Strength

Mexiletine is typically formulated as hard gelatine capsules with the most frequent presentation being 200 mg mexiletine HCl (which corresponds to 167 mg mexiletine strength).

4.2.2 IMP Packaging and Labelling

Not applicable.

Mexiletine will be obtained from the marketplace by the caregiver and/or the treating physician via typical drug prescription process.

Patients/caregivers will be provided with mexiletine prescriptions by the treating physician to last until the next clinically planned visit.

4.2.3 Storage

Mexiletine must be stored at a temperature not exceeding 30°C and away from moisture.

4.3 Mexiletine Supply, and Accountability

The investigator or designee is responsible for ensuring adequate accountability of the study drug. All study drug prescribed to subjects/caregivers must be accurately recorded on an appropriate drug accountability record maintained by the Investigator or designee. Mexiletine should not be used for purposes other than those intended by the treating physician for the treatment of myotonias.

5 STUDY PROCEDURES

All patients/ caregivers / parents or legal representatives must provide their written informed consent and assent before any assessments or evaluations required by the study are performed. All screening assessments must be completed within 2 weeks of informed consent.

The evaluations and assessments during the study will be performed according to routine clinical practice or as necessary for each individual patient according to the treating physician. Consulted clinical experts have recommended that according to standards of care visits are usually performed with a frequency no longer than every 6 months.

There will be a screening visit to ensure the patient complies with all the participation criteria.

5.1 Screening Visit – V0 (Maximum 2 weeks)

The screening procedures will include recording the following parameters which typically have already been collected in the patient's medical history:

- 1. Obtaining written informed consent/ assent as per regulatory requirement
- 2. Patient demographics and anthropometric measurements (age, gender, ethnicity, height, weight)
- 3. Vital signs, including blood pressure (BP), heart (pulse) rate (HR)
- 4. Current medical condition: Type of myotonic disorder (genetic diagnosis), age of symptom onset, family history of myotonic disorders.
- 5. Signs and symptoms of myotonia as documented in medical history.
- 6. Clinical myotonia evaluation appropriate to patient's age and treating physicians standard clinical practice including proposed efficacy assessments and quality of life evaluations, where performed.
- 7. Review of inclusion/exclusion criteria
- 8. Medical history of:
 - Neurological disorders (Seizure, Epilepsy, Vertigo, Headache, Paraesthesia, Dysgeusia, Ataxia)
 - Gastrointestinal disorders (Abdominal pain, Nausea, Vomiting, Diarrhoea, Constipation, Intestinal ulcer, GI bleeding, Dysphagia, Oesophageal ulceration)
 - Renal or hepatic disorders
- 9. Any other significant medical history
- 10. History of unprovoked falling and stumbling, fractures
- 11. History of swallowing difficulties and/or laryngospasm (particularly below 6 months of age) / history of aspirations/ aspirational pneumonia (myotonia of mastication muscles)
- 12. History of hospitalisation due to muscle condition
- 13. History of any cardiac, rhythm disorders.
- 14. Cardiac status at baseline (ECG and echocardiogram (cardiac ultrasound; US), done up to 3 months prior to screening is acceptable. If not done earlier, ECG and echocardiogram to be performed at screening visit)
- 15. Surgical history
- 16. For patients previously prescribed mexiletine, any modification in mexiletine dose/ frequency in addition to the current dose/frequency as prescribed by the treating physician

- 17. History of previous anti-myotonia treatment other than / mexiletine
- 18. Concomitant medications in use (along with dose and frequency)
- 19. Washout for any current/ ongoing medications required/not required
- 20. Collection of known laboratory investigations if performed according to the treating physician regular practice including basic haematology, biochemistry and urinalysis.

Prescription for mexiletine doses for the use until next visit will be dispensed at this visit if the patients/caregivers did not have enough already.

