Protocol No. MEX-NM-401 Version No.: 1.0 Dated: May 30th 2024

Study Drug Dose, Dosage Form, and Mode of Administration

Dosing recommendations for oral administration of mexiletine capsule are still being established and are currently estimated according to the child's body weight. Dosing in this registry study is at the discretion of the treating physician and the clinical response of the patient. No per protocol specific dosing instructions are provided to the treating physician. The Sponsor of this non-interventional registry study is trying to understand how the drug is currently being used in this disease and population and try to establish a benefit:risk assessment.

Administration will be via the oral route, using either capsules or opening and sprinkling contents on food/drink according to the child's age and ability.

Dose suitability with regard to sprinkling contents on food/drink will be assessed.

Study Endpoints and Outcome Variables:

As permitted by clinical practice and patient's age, the following assessments are proposed:

- To assess the efficacy of mexiletine for the treatment of myotonic disorders as assessed by the clinician including as follows (where applicable).
 - Muscle strength measured using the modified Medical Research Council (MRC) scale to evaluate neck flexors, shoulder abductors, elbow flexors and extensors, wrist extensors, finger flexors, hip flexors, knee flexors and extensors, posterior foot flexors and plantar flexors.
 - Clinical Global Impression (CGI) Scores given to caregivers and assessed by the investigators
- To assess long-term safety
 - Number and frequency of adverse events (AEs), serious adverse events (SAEs) and AE leading to treatment discontinuation, throughout the study while on treatment with mexiletine
 - Incidence of adverse events of special interest (AESI), namely:
 - Severe Cutaneous Adverse Reactions (SCARs).
 - Cardiac arrhythmia.
 - Increased frequency of seizure episodes in patients with epilepsy.
- To assess the different routes of administration and formulations of mexiletine used according to clinician's preferences
- To assess safety and efficacy of mexiletine dosing formulations used
- To assess dose and treatment compliance as well as acceptability and palatability of different modes of administration.

Statistical Methods

Sample Size

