The currently approved strength for Namuscla is 200 mg mexiletine HCl formulated as hard capsules for oral use containing 167 mg of mexiletine (NaMuscla SmPC, 2023). The recommended starting dose of mexiletine in adults is 167 mg daily (1 capsule per day). After at least 1 week of treatment, based on the clinical response, the daily dose can be increased to 333 mg daily (2 capsules per day). After at least 1 further week of treatment, based on clinical response, dose can be further increased to 500 mg daily (3 capsules per day). Maintenance treatment is between 167 mg – 500 mg daily (1 to 3 capsules per day), according to the intensity of symptoms and the clinical response, taken regularly throughout the day. The adult daily dose should not exceed 500 mg/day (NaMuscla SmPC, 2023).

As well as the approved 200 mg strength, new paediatric formulations of NaMuscla® were developed consisting of 75 mg and 100 mg strengths with identical qualitative composition to the 200 mg strength. These strengths are not yet authorized. The line extension application is expected to be submitted in April 2025.

Despite reported use and limited data from case studies in the paediatric population, the safety and efficacy of mexiletine in this paediatric population have not yet been established. A recent mini-review of the use of mexiletine in children concluded that special attention by health authorities was needed to maintain access to mexiletine in rare paediatric diseases and further paediatric research was required (Sarret *et al.*, 2024). They specifically mention that off-label

registries for the use of mexiletine in children, especially younger than 6 years, are also required in neuromuscular disorders. The authors admit that although the drug has no proven paediatric indication it has been used in various rare paediatric conditions since the 1970s including heart disorders, neuromuscular diseases, epileptic seizures and pain disorders. Mexiletine has long been reported to be useful in paediatric cardiology and paediatric neurology, with a usual dose ranging between 3 to 15 mg/kg/day (see also section 1.4 Regulatory background).

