Data will be entered at baseline upon patient enrolment and entered periodically thereafter for all routine clinical practice patient visits. For example, all laboratory values collected at routine clinical visits occurring between month 6 and month 12 of a patient's participation in the registry should be entered at the 12-month time point. All data will include the date each assessment was performed. Where available, additional retrospective data will be collected. Retrospective data will be focussed primarily on patterns of mexiletine use and dose adjustments as well as any efficacy assessments. Retrospective safety data will also be recorded, especially in relation to any AEs that affect dosing, SAEs or AESIs, but there will be no requirement to report any retrospective AEs prior to signing the informed consent. In cases where retrospective data are captured, this will be recorded from first mexiletine prescription up to the baseline visit or to the maximum age of eligibility for entering into the trial (that is, up to 6 years). For eligible patients who provide informed consent, data elements will be extracted from the information routinely recorded in the medical records and transcribed in to the electronic Case Report Forms (eCRF). Safety, treatment administration and efficacy assessments will be collected during the visits. AEs will be collected from the time informed consent is given to end of treatment.

No drug safety monitoring committee (DSMB) will be created.

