6.2 Secondary Variables

- Description over time of outcomes of mexiletine use including dosing, formulation used, method of administration, acceptability and palatability as per the data collected by the treating physician according to age and cohort.
- The treating physician with elaborate a brief text with risk-benefit conclusions using the information from both the primary and secondary variables.

ASSESSMENT OF EFFICACY

Data Interpretation of Instruments/Scales

The efficacy endpoints chosen for the study are based on those that have been commonly used during routine clinical practice in adults (Logigian *et al.*, 2010; Statland *et al.*, 2012a; Statland *et al.*, 2012b), but they have been adapted according to the patient's age and ability to participate in the efficacy evaluation. Moreover, the approach to and the scope of efficacy endpoints has been accepted by the Regulatory Authorities (in particular the Paediatric Committee; PDCO) during the evaluation and discussion on the paediatric investigation plan (PIP) that this protocol is specifically designed to support. However, in this observational study the performance of these tests is not mandated by protocol or pre-scheduled. They will only be performed during the study according to routine clinical practice for the treatment of patients with myotonias at the discretion of the treating clinician.

I. Faces scale

A Faces (or other symbol) self-reported scale for children aged 6 years will be used to score muscle stiffness (myotonia severity) as by the patient. This type of scale has been validated and is considered suitable for use in at least a subset of the age group proposed (Tsze *et al.*, 2013). Muscle stiffness is commonly used as either a primary or secondary measure of efficacy in myotonic disorders clinical trials.

Similarly, the Faces scale will be used to assess pain, weakness and tiredness in study participants as secondary endpoints. As above, the Faces for severity score of pain, weakness and tiredness as self-reported will be constructed the same as for the stiffness score with a 10 cm straight horizontal line having the endpoints "no [symptom] at all" and "[symptom] as worst possible

II. Hand Grip Myotonia Test

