8.3 Physical and Systemic Examination

A physical examination will be performed at the time of screening to ensure patients comply with participation criteria. Other physical and or systemic examinations will be performed according to regular clinical practice or at the discretion of the treating physician.

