8.4 Vital Signs

Vital signs, including blood pressure (BP), heart (pulse) rate (HR) will be measured according to regular clinical practice or at the discretion of the treating physician.

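### Body weight is named for collection only at screening, so dose relative to weight over two years of growth is not assured to be derivable

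*Protocol*

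**What the plan says.** Section 5.1, item 2, lists "Patient demographics and anthropometric measurements (age, gender, ethnicity, height, weight" for the screening visit. This is the only place where the protocol names weight as something to be collected.

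The later records are described without it:

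- **Data elements (synopsis and section 3.2).** The list runs from demographics and genetics to organ manifestations; section 3.2 adds the pattern of mexiletine use. Data are to be "entered periodically thereafter for all routine clinical practice patient visits".
- **Dose changes and dose capture (4.1.1.1 and 4.1.4).** Escalations and reductions go in the CRF. Capsule count or powder amount, strength and vehicle are captured. No weight accompanies any of these.
- **Examinations (8.3).** "Other physical and or systemic examinations will be performed according to regular clinical practice", with no content specified.
- **Vital signs (8.4).** "Vital signs, including blood pressure (BP), heart (pulse) rate (HR) will be measured according to regular clinical practice".

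The protocol nevertheless ties dose to weight. The synopsis says dosing recommendations "are still being established and are currently estimated according to the child's body weight". Section 1.2 reports paediatric use "with a usual dose ranging between 3 to 15 mg/kg/day". Section 6.2 sets as a secondary variable the "Description over time of outcomes of mexiletine use including dosing, formulation used, method of administration", to be described by age and cohort. Section 1.3 gives support for dosing and labelling as a reason for generating paediatric data. Pharmacokinetics do not apply (5.2 and section 7).

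On units, section 4.2.1 describes the usual capsule as "200 mg mexiletine HCl (which corresponds to 167 mg mexiletine strength".

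**The concern.** Patients enter between birth and just under 6 years and stay at least two years, so weight can change a great deal between the screening record and a later dose record. If the registry transcribes doses but not weights, dosing over time can be reported only in absolute mg or against an outdated weight.

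Both can mislead. Divided by screening weight, a dose that merely keeps pace with growth looks like escalation, and a fixed mg dose looks constant although mg/kg is falling. Absolute mg avoids that error but is hard to compare between a neonate and a 5-year-old when the protocol says doses are estimated from weight. No plasma concentrations are taken that could substitute.

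Retrospective records have the same gap. Section 3.2 focuses them on use and dose adjustment from the first prescription, again without asking for the weight at that time.

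This is a question of what is collected, so it cannot be left to the analysis plan. The planned minimum is 10 evaluable patients, 4 of them under 6 months at entry (section 8.8). One Cohort 2 patient without usable weights is 1/4 = 25% of that cohort's minimum.

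**Working it through.** **1. The protocol's own conversion.** Sections 1.2 and 4.2.1 equate 200 mg of hydrochloride with 167 mg of mexiletine.

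- 200/167 = 1.198, and 167/200 = 0.835.
- One, two and three capsules at 167 mg give 167, 334 and 501 mg, against the stated 167, 333 and 500 mg. The figures agree to rounding.
- Section 1.3 gives 200, 400 and 600 mg/day for the adult placebo-controlled trial without naming salt or base. 600 × 0.835 = 501 mg, so this series fits the same capsule counts expressed as salt. The two series do not conflict.

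**2. Error from using screening weight after baseline.** Let D be the daily dose, W0 the weight at screening, W the weight when the dose is given, and g = W/W0.

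- True value = D/W. Apparent value = D/W0.
- Apparent/true = W/W0 = g, so the overstatement is g − 1.

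The documents give no growth data, so g is an assumption, shown over a range:

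| Assumed g | Overstatement of mg/kg | True mg/kg/day that would read as 15 |
|---|---|---|
| 1.2 | 20% | 15/1.2 = 12.5 |
| 1.5 | 50% | 15/1.5 = 10.0 |
| 2 | 100% | 15/2 = 7.5 |
| 3 | 200% | 15/3 = 5.0 |

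The value 15 is the upper end of the range cited in section 1.2 and serves here only as a yardstick.

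**3. Retrospective dose records.** Here screening weight is the later and larger one. If weight grew by a factor g between the dose record and screening, apparent/true = 1/g. For g = 1.2 this is 0.83 (17% too low). For g = 3 it is 0.33 (67% too low). The error changes sign at baseline, so a series spanning baseline would be distorted in both directions.

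**4. Unit ambiguity (minor).** The cited 3 to 15 mg/kg/day carries no salt or base label.

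- If it is salt, it equals 3 × 0.835 = 2.5 to 15 × 0.835 = 12.5 as base.
- If it is base, it equals 3 × 1.198 = 3.6 to 15 × 1.198 = 18.0 as salt.
- A mix-up in a recorded dose would shift it by +19.8% or −16.5%, at baseline as much as later.

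**The case against.** The strongest reply is that this is a non-interventional registry governed by routine practice. It has no itemised follow-up schedule, so the absence of an item from one proves little. Section 3.2 has routine-visit data transcribed with dates. Its data elements open with demographics, which section 5.1 groups with height and weight. The vital signs wording is not exhaustive. Weight may well be in the notes.

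This stands in part. A reader might infer that weights after screening will not exist, or that entry weight must be used for every later dose. The protocol says neither. What remains is that nothing requires weight to be transcribed, and the demographics entry is too loose to secure it.

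A second reply is that no mg/kg variable is defined: section 6.2 says dosing and section 3.2 says dose and frequency. That is correct, so the registry cannot be said to be bound to report a weight-based dose. But weight is the protocol's own stated basis for paediatric dosing, and a description of dosing by age and cohort needs it to be interpretable.

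Third, a reader might infer that adverse events and efficacy would be set against the wrong exposure. The planned analyses do not support this: sections 8.13 and 8.14 contain no table by dose level.

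Finally, the salt/base question is an ambiguity and not an error. Capsule count, strength and formulation are all captured (4.1.1, 4.1.4, 6.2) and will usually settle the unit.

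**Conclusion.** The point holds as a data-collection gap. Weight is named only at screening, while dosing is to be described over at least two years in children who may enter as neonates. Dose relative to weight is therefore not assured to be derivable after baseline or, for retrospective records, before it.

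If screening weight were used by default, later mg/kg would be overstated by 20% to 200% for assumed growth of 1.2- to 3-fold. Those growth factors are assumptions; only the salt/base factor of 1.20 comes from the protocol. If sites transcribe weight unprompted, the gap closes in practice, but the protocol does not secure this.

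The effect is on the secondary description of dosing and on what it can contribute to dosing and labelling. No planned safety or efficacy table is shown to be wrong, and nothing here bears on which dose is appropriate.

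**What to change.** - **Section 3.2 and the synopsis:** add dated body weight, transcribed from routine notes where recorded, to the data elements for each routine visit and each recorded dose change. Include retrospective dose records where a weight is available.
- **Section 6.2:** describe dosing both as mg/day and as mg/kg/day, using the weight nearest in time to the dose record.
- **Minor addition, section 4.1.4 and the eCRF:** record product and labelled strength, and report all doses in one stated unit, salt or base.

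The main cost is one more dated field to transcribe, plus small eCRF additions for product and unit. No extra visit or procedure is needed. Some values will be missing where weight was not charted; under section 8.10 they stay missing, and the number of dose records with a usable weight should be shown beside the mg/kg summaries.
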